**Table 3. Anterior Chamber Flare Grading Scale**

[figure not shown]
Grade	Description
0	None
1+	Faint
2+	Moderate (iris and lens details clear)
3+	Marked (iris and lens details hazy)
4+	Intense (fibrin or plastic aqueous)

The results will be summarized using counts and percentages for each treatment group at each visit for each eye (first eye, second eye, and all eyes separately) using the Safety Set. Percentages will be based on the number of unique eyes in each treatment group with responses. Shift tables for anterior chamber cells and flare will also be provided comparing each follow-up visit to baseline for first operative eyes, second operative eyes, and all operative eyes separately.

A subject listing containing the results of the anterior chamber cells and anterior chamber flare assessments will also be provided.

#### **16.4 Corneal Edema**

Corneal edema assessments will be performed at each visit, except for the operative visits. Corneal edema will be graded according to the scale described in Table 4.

**Table 4. Corneal Edema Grading Scale**

Amount	Grade	Description
None	0	Normal transparency: a. No epithelial or sub-epithelial haziness b. No microcysts c. No stromal cloudiness
Trace	+1	a. Barely discernible localized epithelial or sub-epithelial haziness, and/or b. 1 to 20 microcysts, and/or c. Barely discernible localized stromal cloudiness
Mild	+2	a. Faint but definite localized or generalized epithelial, sub-epithelial or stromal haziness/cloudiness, and/or b. 21 to 50 microcysts
Moderate	+3	a. Significant localized or generalized epithelial, sub-epithelial or stromal haziness/cloudiness, and/or b. 51 to 100 microcysts
Severe	+4	a. Definite widespread epithelial or stromal cloudiness, giving dull glass appearance to cornea or numerous coalescent bullae (note number and location of bullae), and/or b. >100 microcysts or bullae, and/or c. Numerous striae (note the number and location of striae or folds)

The results will be summarized using counts and percentages for each treatment group at each visit for each eye (first eye, second eye, and all eyes separately) using the Safety Set. Percentages will be based on the number of unique eyes in each treatment group with responses. Shift tables for corneal edema will also be provided comparing each follow-up visit to baseline for first operative eyes, second operative eyes, and all operative eyes separately.

### 16.5 Posterior Capsule Opacification

Posterior capsule opacification (PCO) will be assessed at every post-operative visit. PCO will be graded according to the scale described in Table 5.

**Table 5. Posterior Capsule Opacification Grading Scale**

Amount	Grade	Description
None	0	No evidence of PCO. Bright red reflex.
Trace	+1	Some loss of transparency involving the posterior capsule visible on retroillumination. Red reflex fairly bright.
Mild	+2	Mild loss of transparency with cloudiness extending through most of the posterior capsule. There may be a few Elschnig's pearls in the posterior capsule.
Moderate	+3	Moderate loss of transparency with difficulty visualizing the retina. There may be multiple Elschnig's pearls in the posterior capsule. Red reflex markedly diminished.
Severe	+4	Posterior capsule very opaque with inability to view the retina. The posterior capsule may have confluent Elschnig's pearls and fibrous scarring. Red reflex barely visible.

During the posterior capsule opacification assessment, whether the subject has undergone an Yttrium Aluminum Garnet (YAG) capsulotomy (yes/no) will also be recorded.

[figure not shown]
The results will be summarized using counts and percentages for each treatment group at each visit for each eye (first eye, second eye, and all eyes separately) using the Safety Set. Percentages will be based on the number of unique eyes in each treatment group with responses.

A subject listing of PCO assessment results will also be provided.

## 16.6 IOL Observations and Glistenings

IOL observations and assessments of IOL glistening will be recorded at every post-operative visit. The results will be graded as described below and on Table 6:

- IOL Observations
  - Does the IOL have scratches or cracks? (Yes/No)
  - Does the IOL have surface haze? (Yes/No)
  - Does the IOL have optic discoloration? (Yes/No)
  - Is the IOL clear? (Yes/No)
- IOL Glistenings

**Table 6. IOL Glistenings Grading Scale**

Grade	Description
Trace	Fewer than 10
1+	10 to 20
2+	20 to 30
3+	30 to 40
4+	More than 40

The results will be summarized using counts and percentages for each treatment group at each visit for each eye (first eye, second eye, and all eyes separately) using the Safety Set. Percentages will be based on the number of unique eyes in each treatment group with responses.

A subject listing of IOL observation results will also be provided.

### **16.7 Manifest Refraction**

Manifest refraction parameters, including sphere (D), cylinder (D), axis (degrees), and spherical equivalent (D), at 4 m will be collected at Preoperative Visit 0, Week 1 (Post-Operative Visit 2A/2B), Month 1 (Post-Operative Visit 3A/3B), Month 6 (Post-Operative Visit 4) and Month 12 (Post-Operative Visit 5).

Spherical equivalent (D) will be computed using the following formula:

$$\text{Spherical Equivalent} = \text{Sphere} + 0.5 * \text{Cylinder}$$

The actual values and changes from baseline for the manifest refraction parameters will be summarized using continuous summary statistics for each treatment group at each visit for each eye (first eye, second eye, and all eyes separately) for the Safety Set.

[figure not shown]
A subject listing of manifest refraction parameters will also be provided.

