### **8.4 Data Analysis Conventions**

All data analysis will be performed by [REDACTED]. Statistical programming and analyses will be performed using SAS® version 9.4 or higher. Output will be provided in rich text format (RTF) for tables and portable document format (PDF) for tables, listings, and figures using landscape orientation.

Summaries for continuous and ordinal variables will include the number of observations (n), arithmetic mean, SD, median, minimum, and maximum. Minima and maxima will be reported with the same precision as the raw values; means and medians will be presented to one additional decimal place than reported in the raw values. Standard deviations will be presented to two additional decimal places than reported in the raw values. Summaries for discrete variables will include counts and percentages. All percentages will be rounded to one decimal place (i.e., XX.X%). Differences between test and control treatment groups will be calculated as test minus control and change from baseline will be calculated as follow-up visit minus baseline.

All statistical tests will be one-sided with a significance level of 0.05 ( $\alpha = 0.05$ ), except for the two superiority tests of DCIVA and DCNVA which will be two-sided with a significance level of 0.05. Correspondingly, confidence intervals (CI) for differences between treatment groups will be two-sided at 90% or 95% confidence. All p-values will be rounded to 4 decimal places; p-values less than 0.0001 will be presented as “<0.0001”; p-values greater than 0.9999 will be presented as “>0.9999.”

Unless otherwise specified, summaries will be presented by treatment group and, where appropriate, visit. Listings will be presented by subject number, treatment group, visit/time point, and parameter as applicable.

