## **10.2 Baseline Disease Characteristics**

Baseline clinical parameters will include potential visual acuity (logMAR), target refraction sphere (D), target refraction cylinder (D), target refraction axis (degrees), IOL power calculation (D), axial length (mm), and anterior chamber depth (mm). Baseline clinical parameters will be summarized at the eye level for the AAS by treatment group and for all subjects using continuous summary statistics.

Subject listings for the baseline clinical parameters above, as well as corneal topography and urine pregnancy test results, will be provided.

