## **12. Operative Procedures**

Operative procedure data will be recorded at the operative visit for each eye. The operative parameters include incision size (mm), incision axis (degrees), incision type (corneal, limbal, other), lens extraction method (phacoemulsification, other), capsulotomy shape (continuous curvilinear capsulorhexis, other), position of the haptics (in the bag, partially in the bag, in the sulcus, uncertain), IOL power, whether the subject experienced any intraoperative complications, and whether any SSIs were performed.

Operative procedure variables will be summarized at the eye level by treatment group using discrete or continuous summary statistics, as appropriate, for the Safety Set. A listing of the operative variables will also be provided for each subject for each eye.

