#### **16.13 Keratometric Measurements**

Keratometric measurements will be collected during the Pre-Operative Visit, Month 1 (Post-Operative Visit 3A/3B), Month 6 (Post-Operative Visit 4), and Month 12 (Post-Operative Visit 5).

Keratometric measurements (K1 [D], K1 Axis [degrees], K2 [D], and K2 Axis [degrees]) will be summarized using continuous summary statistics for each treatment group and for all actively treated subjects at each visit for each eye (first eye, second eye, and all eyes separately) for the Safety Set.

A subject listing of keratometric measurements will be provided.

17. [REDACTED]

17.1 [REDACTED]

[REDACTED]  
[REDACTED]  
[REDACTED]  
[REDACTED]

[REDACTED]  
[REDACTED]  
[REDACTED]

[REDACTED]:

17.3

18. [REDACTED]

[REDACTED]

[REDACTED]

[REDACTED]

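### The SAP gives refraction, keratometry and target axes ordinary means and SDs (and subtracted changes for refraction axis), which misstates them whenever axes lie on both sides of 0/180 degrees

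*SAP*

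**What the plan says.** SAP 16.7 includes axis in the refraction data: "Manifest refraction parameters, including sphere (D), cylinder (D), axis (degrees), and spherical equivalent (D), at 4 m will be collected" at the preoperative visit and at Visits 2 to 5. It then applies one rule to all of these parameters: "The actual values and changes from baseline for the manifest refraction parameters will be summarized using continuous summary statistics". Axis is not excepted.

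SAP 16.13 names the flat and steep keratometry axes explicitly. Its list of measurements ends with "K2 Axis [degrees]) will be summarized using continuous summary statistics", by treatment group, visit and eye. It asks for actual values only, not changes.

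SAP 10.2 lists the target refraction axis, in degrees, among the baseline clinical parameters and gives all of them continuous summaries.

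SAP 8.4 says what a continuous summary is: "Summaries for continuous and ordinal variables will include the number of observations (n), arithmetic mean, SD, median, minimum, and maximum". It also defines change: "change from baseline will be calculated as follow-up visit minus baseline".

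SAP 12 records incision axis in degrees, but lets each operative variable be shown by discrete or continuous statistics, whichever suits it.

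No readable section gives a circular or vector method, a rule for wrapping an axis change, or an exception for axis.

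**The concern.** An astigmatic axis is a direction without a sense: 0 and 180 degrees are the same axis. The recorded number therefore jumps at 0/180 although nothing jumps in the eye. An arithmetic mean across that point lands far from every eye in the sample, and can come out perpendicular to the true direction. A subtraction across it can turn a small rotation one way into a very large one the other way.

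The SAP states a rule, and the rule gives wrong numbers for part of the scale, so this is more than a missing detail. The affected tables repeat by arm, by visit, and for first, second and all eyes. A reader who uses them to judge residual or corneal astigmatism, for example as background to uncorrected acuity, would be misled about its direction, spread and stability.

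**Working it through.** **Inputs.** The rules are those of SAP 8.4, 10.2, 16.7 and 16.13. The documents state no figure on this point, so there is none to reproduce. They also give no axis distribution, so every distribution below is an assumption. The group size in the simulation, 334 eyes, is the planned test arm in SAP 5.

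**Comparator.** Double each angle, average the cosines (C) and sines (S), and halve the resulting angle. With R = sqrt(C² + S²), the circular SD is half of sqrt(-2 ln R), in degrees. Axis changes are wrapped to -90 to +90.

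**Small examples**

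- *Axes 5 and 175 (10 degrees apart).* SAP rule: mean (5 + 175)/2 = 90; SD = sqrt(85² + 85²) = 120.2. Circular: doubled angles 10 and 350, so S = 0 and C = R = cos 10° = 0.985; mean 180 (the same as 0), SD 5.0.
- *Axes 2, 5, 10, 170, 175, 178.* SAP rule: mean 540/6 = 90, median (10 + 170)/2 = 90, SD 92.5. Circular: mean 180, SD 6.6. The median does not rescue the table.
- *Change from 175 to 5.* SAP rule: 5 - 175 = -170. Wrapped: -170 + 180 = +10.

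**Simulation** (334 eyes, 4,000 runs; assumed true change +5, SD 10)

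| Assumed centre, spread | SAP mean axis (SD) | SAP mean change (SD) | Eyes with apparent change above 90 |
|---|---|---|---|
| 0/180, 10 | 90.0 (82.3) | -19.9 (85.1) | 26.9% |
| 0/180, 20 | 89.9 (75.0) | -10.9 (67.0) | 16.3% |
| 0/180, 30 | 90.0 (68.5) | -6.3 (56.7) | 11.4% |
| 15, 20 | 55.8 (62.5) | -2.4 (56.2) | 11.0% |
| 45, 20 | 47.2 (23.7) | 5.1 (20.1) | 1.2% |
| 90, 20 | 90.0 (20.0) | 5.0 (10.1) | 0.0% |

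The wrapped change is 5.0 (SD 10.0) in every row.

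**Check by hand of the 0/180, spread 20 row**

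- *Mean and SD.* Let x be the signed distance from 0. Half the eyes are recorded as |x| and half as 180 - |x|, so the mean is 90. The variance is 90² - 180·E|x| + 20², with E|x| = 20·sqrt(2/π) = 15.96. That is 8100 - 2872 + 400 = 5628, so the SD is 75.0.
- *Change.* Each upward crossing of 0/180 subtracts 180 from the true change and each downward crossing adds 180. The expected reported change is 5 + 180·[P(post < 0) - P(pre < 0)]. The post value has mean 5 and SD sqrt(20² + 10²) = 22.36, so P(post < 0) = Φ(-0.224) = 0.4115. Then 5 + 180·(0.4115 - 0.5) = 5 - 15.9 = -10.9, as simulated.

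**Keratometry.** In a regular cornea the flat and steep meridians are about 90 degrees apart, and Protocol 5.2 excludes irregular corneal astigmatism. If one of the K1 and K2 axes clusters safely near 90, the other straddles 0/180. A favourable sample is therefore unlikely to protect both keratometry rows.

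**The case against.** The strongest reply is that little depends on these tables. Both co-primary effectiveness endpoints and the secondary one are best-corrected or distance-corrected acuities. Uncorrected acuity and spectacle independence are additional variables, and no section uses the axis tables to interpret them. Eyes with keratometric astigmatism above 1.0 D are excluded, and raw values remain in subject listings. All of this stands, and it limits the point to descriptive reporting. It does not make the tabulated values right.

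A second reply is that the harm depends on the sample. That also stands. A reader might infer that every axis table will be wrong, or that a group recorded entirely at 180 would be reported near 90. Neither follows: identical readings of 180 average to 180, and axes centred at 90 with a spread up to 20 degrees are summarised correctly. The error needs axes on both sides of 0/180.

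Two other extensions are tempting and are not supported:

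- *Incision axis.* SAP 12 does not fix a mean, because discrete summaries are already allowed. The documents also do not say whether incision position is recorded over 180 or 360 degrees.
- *Sphere and cylinder.* These are dioptre quantities whose means and changes are valid scalar summaries, and spherical equivalent is already derived. Vector reporting would add direction, but its absence makes none of those values wrong.

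Finally, SAP 17 and 18 are redacted and the table list is not shown, so the planned table layouts cannot be checked. The explicit text of 10.2, 16.7 and 16.13 still governs as written.

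**Conclusion.** The point holds for manifest refraction axis and its change from baseline, for the K1 and K2 axes, and for the target refraction axis. As written, the SAP calls for statistics that give a false centre and spread wherever axes fall on both sides of 0/180 and, for refraction, a false change.

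The size depends on assumed distributions. With axes centred at 0/180 and a spread of 10 to 30 degrees, the reported mean is about 90 with an SD of roughly 69 to 82. A true change of +5 is reported with the wrong sign, between about -20 and -6. With axes near 90 the effect is negligible.

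A reader might infer that the effectiveness or safety conclusions are at risk. They are not: no endpoint, hypothesis test, power figure or success rule uses axis. The change is still worth making, because the flaw is known in advance and cheap to remove.

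**What to change.** - **SAP 10.2, 16.7 and 16.13:** state that axis is excluded from the continuous summaries, so that no arithmetic mean, SD or change is produced for it. Keep axis in the subject listings, which are already planned.
- **Direction of astigmatism:** summarise it in one of two ways. The first is power vectors, J0 = -(C/2)·cos(2 × axis) and J45 = -(C/2)·sin(2 × axis), where C is the cylinder, with their changes for refraction. For keratometry, derive C from K1 and K2 under a stated sign convention. The second is counts of with-the-rule, against-the-rule and oblique eyes, with the cut-points fixed in the SAP.
- **Any axis change that is still reported:** wrap it to -90 to +90 degrees.
- **SAP 12:** for incision axis, choose the discrete option that the text already allows, such as sector counts, and state the recording range.
- **No change needed:** the summaries of sphere, cylinder and spherical equivalent can stay.

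The cost is a few lines of SAP wording, one derived-variable step and revised table shells. No new data are needed.

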### **16.8 Pupil Size**

Pupil size will be measured using a pupil gauge with measurement accuracy of 0.5 mm at Preoperative Visit 0, Month 6 (Post-Operative Visit 4), and Month 12 (Post-Operative Visit 5). For the mesopic and photopic pupil size measurements, lighting conditions will be identical to those used for mesopic and photopic contrast sensitivity testing, respectively. Subjects will initially dark adapt for 10 minutes prior to mesopic pupil size measurements.

The actual values and changes from baseline for pupil size (mesopic and photopic) will be summarized using continuous summary statistics and the pupil size categorizations used in subgroup analyses [( $\leq 4$  mm,  $> 4$  mm) and ( $\leq 2.5$  mm,  $> 2.5$  mm to  $< 4$  mm,  $\geq 4$  mm)] will be summarized using counts and percentages for each treatment group at each visit for each eye (first eye, second eye, and all eyes separately) for the Safety Set.

A subject listing of pupil size will also be provided.

### 16.9 Dilated Fundoscopy Examination

A dilated fundoscopy examination of the vitreous, retina, macula, and optic nerve as well as an assessment of the cup-to-disc (C/D) ratio will be performed for first and second operative eyes at Preoperative Visit 0, Month 1 (Post-Operative Visit 3A/3B), Month 6 (Post-Operative Visit 4) and Month 12 (Post-Operative Visit 5). The results will be graded as normal or abnormal.

For subjects implanted with a multifocal IOL, gradings of the clarity of the retinal image through the multifocal IOL compared to previous monofocal IOL experience will be recorded as described on Table 7.

**Table 7. Clarity of the Retinal Image Grading Scale**

Grade	Description
1	Poor clarity compared to view through monofocal IOL.
2	Fair clarity compared to view through monofocal IOL.
3	Good clarity compared to view through monofocal IOL.
4	Excellent clarity compared to view through monofocal IOL.

The dilated fundoscopy results of the vitreous, retina, macula, and optic nerve will be summarized using counts and percentages for each treatment group at each visit for each eye (first eye, second eye, and all eyes separately) using the Safety Set. Percentages will be based on the number of unique eyes in each treatment group with responses. Shift tables for dilated fundoscopy will also be provided comparing each follow-up visit to baseline for first operative eyes, second operative eyes, and all operative eyes separately.

C/D ratio will be summarized using continuous summary statistics for each treatment group at each visit for each eye (first eye, second eye, and all eyes separately) for the Safety Set.

Gradings of the clarity of the retinal image will be summarized using counts and percentages for the FINEVISION HP treatment group at Month 1 (Post-Operative Visit 3A/3B), Month 6 (Post-Operative Visit 4) and Month 12 (Post-Operative Visit 5) for each eye (first eye, second eye, and all eyes separately) for the Safety Set.

A subject listing of the dilated fundoscopy results will also be provided.

### 16.10 Intraocular Pressure (IOP)

Intraocular pressure (IOP) will be assessed using Goldmann applanation tonometry at all visits, except for the operative visits (Operative Visit 0A/0B). Results will be recorded in mmHg. If more than one measure is obtained for a protocol specified visit, the mean IOP value will be used for the summaries.

The IOP actual values and changes from baseline will be summarized using continuous summary statistics for each treatment group at each visit for each eye (first eye, second eye, and all eyes separately) for the Safety Set.

A subject listing of IOP will also be provided.

#### **16.11 IOL Tilt and Decentration**

Evaluation of tilt and decentration will be performed with the pupil dilated at Day 1 (Post Operative Visit 1A/B), Week 1 (Post Operative Visit 2A/B), Month 1 (Post Operative Visit 3A/B), Month 6 (Post Operative Visit 4), and Month 12 (Post Operative Visit 5).

Tilt will be recorded in degrees and decentration will be recorded in millimeters.

IOL tilt and decentration will be summarized using continuous summary statistics for each treatment group at each visit for each eye (first eye, second eye, and all eyes separately) for the Safety Set.

A subject listing of IOL tilt and decentration will also be provided.

#### **16.12 Device Deficiencies**

Device deficiencies will be presented in a data listing.

#### **16.13 Keratometric Measurements**

Keratometric measurements will be collected during the Pre-Operative Visit, Month 1 (Post-Operative Visit 3A/3B), Month 6 (Post-Operative Visit 4), and Month 12 (Post-Operative Visit 5).

Keratometric measurements (K1 [D], K1 Axis [degrees], K2 [D], and K2 Axis [degrees]) will be summarized using continuous summary statistics for each treatment group and for all actively treated subjects at each visit for each eye (first eye, second eye, and all eyes separately) for the Safety Set.

A subject listing of keratometric measurements will be provided.

17. [REDACTED]

17.1 [REDACTED]

[REDACTED]  
[REDACTED]  
[REDACTED]  
[REDACTED]

[REDACTED]  
[REDACTED]  
[REDACTED]

[REDACTED]:

17.3

18. [REDACTED]

[REDACTED]

[REDACTED]

[REDACTED]

## 19. Changes from Protocol-Stated Analyses

The SAP includes the following changes from the protocol-stated analyses:

1. [REDACTED]

[REDACTED]

[REDACTED]

[REDACTED]

3. The reason for missing data “withdrawal due to investigator’s request” from the protocol has been updated to “withdrawal due to physician decision” in the SAP to match the corresponding reason for discontinuation term from the end of study eCRF.
4. Summaries of AEs by investigator from the protocol have been updated to summaries of AEs by site in the SAP.
5. Pupil size subgroups for sub-group analyses of primary and secondary effectiveness and safety endpoints have been updated from ( $\leq 4\text{mm}$ ,  $> 4\text{mm}$ ) in the protocol to small ( $< 2.5\text{ mm}$ ), medium ( $2.5\text{ to } \leq 4\text{mm}$ ), and large ( $> 4\text{ mm}$ ) in the SAP per sponsor request. Pupil size subgroup analyses of the secondary safety endpoints and overall adverse events were added to the SAP to address FDA comments requesting safety and effectiveness subgroup analyses by pupil size.

[figure not shown]
